7.0 Randomized Controlled Trial

7.1 Primary Aim:

Among 80 PrEP eligible patients compare in a pilot 1:1 RCT design, the strategies of a) facilitated linkage for PrEP initiation within 14-days of ED visit and b) immediate PrEP (iPrEP) initiation in the ED, a 14-day PrEP starter pack at discharge and facilitated linkage.

The primary outcome is PrEP usage at 90 days post PrEP initiation visit. Secondary outcomes include retention in care, STI diagnosis, risk behavior and PrEP adherence at 30, 60, and 90 days.

7.2 Secondary/Exploratory Aims:

- (1) Retention in care at 30 and 60 and 90 days post PrEP initiation
- (2) PrEP usage at 30 and 60 days post PrEP initiation
- (3) PrEP adherence at 30, 60, and 90 days post PrEP initiation
- (4) Risk behavior at 30, 60, and 90 days post PrEP initiation
- (5) STI diagnoses at 30, 60 and 90 day follow-up visits
- (6) HIV infection
- (7) Program satisfaction

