Patients will be instructed at the time of discharge that they will be contacted by a member of the PrEP Warm Line to schedule follow-up with a PrEP provider. The decision to start PrEP for those not randomized to the iPrEP arm or to stop or continue PrEP for those randomized to the iPrEP arm will be a decision made by the patient in conjunction with their PrEP provider. The ED clinical team will be available to assist patients should have they have any concerns or problems before that linkage occurs. For those randomized to the iPrEP arm if they have any side-effects within the first 14-days of starter pack use they will contact the study team and a decision to continue or stop PrEP will be made after a discussion between the patient and the PI. All patients enrolled in the study will receive standard PrEP counseling which includes information about the need for frequent HIV testing and risk reduction strategies. The importance of follow-up with the PrEP provider will be stressed. We do not anticipate the need for any re-testing (HIV, LFTs, eCrCL) by the study team after ED discharge. These tests are not typically recommended until the patient has been on PrEP for at least 30 days and sometimes not until 90-days. All recommended follow-up testing will be the responsibility of the clinical PrEP provider.

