9.5 Follow-up

All follow-up assessments will be performed over the phone. Follow-up assessments will occur at 30, 60, and 90 days post enrollment.

Follow-up assessments will include:

- 1) Attitudes toward Pre-Exposure Prophylaxis Scale (APS) (Appendix 3)
- 2) Section 4 of ICAP "Screening for Substantial Risk of HIV" (Appendix 5)
- 3) Satisfaction questionnaire and qualitative assessment and visit specific satisfaction instrument (VSQ-9) (Appendix 6)
- 4) Adherence information measured by (1) self-report. Self-report will be assessed with the single measure Guidelines Regimen Information Program (GRIP) guide and questions on last dose and number of missed doses since prior follow-up. (Appendix 7)
- 5) CDC Sexual Behavior Questions (CSBQ) (Appendix 4)
- 6) STAR*D PRISE (Side-effect assessment)

Assessment of engagement in PrEP care at 30, 60, and 90 days post enrollment will be verified by direct contact with the treatment provider/program provided or by EMR review if the patient is linked within the Mount Sinai Health System. If the patient is receiving their PrEP care outside of the Mount Sinai Health System, a signed release authorization form will be sent.

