11.1.2 Analysis of Primary and Secondary Outcomes

Analysis will be on an intention-to-treat basis. In statistical analyses, participants will be included to the date of their last active follow-up visit. Comparisons between control and experimental (iPrEP) arms. To assess the success of randomization, a summary of the baseline variables by treatment group will be tabulated and univariate comparisons performed. The primary outcome, retention in care and PrEP usage, will be compared with proportions and Fisher's exact derived confidence intervals. Secondary outcomes: Secondary analysis will focus on determining how retention in care, risk behavior, adherence or STI diagnosis differ between the groups at any of the follow-up time points. PrEP adherence based on pill counts will be calculated by dividing the number of pills taken by the number of pills prescribed. Adherence will be calculated by study month for each participant. Group adherence comparisons will be compared using Wilcoxon rank sum test. Retention in care, STI diagnosis and risk behavior at each time point will be analyzed for each study visit. Retention in care and STI diagnosis will be treated as dichotomous variables for analysis. Measures of risk behavior will include consistency of condom use and number of sexual partners since prior study visit. Condom use will be treated as an ordinal variable and number of sexual partners as a continuous variable for analysis.

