12.2. Study Procedures, Materials, and Potential Risks

Aim 1

Study Procedures: Patients found to be eligible for PrEP will be randomized to immediate PrEP (iPrEP) initiation using a 14-day starter pack or PrEP initiation in the outpatient clinic. Both groups will have facilitated linkage to care. Follow-up study visits will occur at 30, 60 and 90days post PrEP initiation. The 30, 60 and 90 day assessments will over the phone.

Effective Date: 4/20/2021

End Date: 3/18/2022

Risks: Aim 1 involves randomization to one of two different PrEP initiation programs. PrEP initiation carries risks that would be considered more than minimal. Patients in both groups will be prescribed tenofovir disoproxil fumarate (FTC/TDF) which will be used for women and transgender men or

emtricitabine/tenofovir alafenamide (FTC/TAF) which will be used for men and transgender women. Both of these medications are FDA approved and is being used for its intended purpose in the population for whom it is indicated. Known physical risks of emtricitabine/tenofovir disoproxil fumarate and emtricitabine/tenofovir alafenamide are impaired renal function, intolerable side effects including nausea, vomiting or diarrhea as well as hypersensitivity reaction and osteopenia with long term use. Patients will also be subject to the same psychological and privacy and confidentiality risks.

Sources of Data: Aim 1 data sources will come from the following

- 1) Socio-demographic questionnaires collected during screening and enrollment
- 2) Behavioral risk factor questionnaires collected at enrollment and 30, 60, and 90day follow-up
- 3) PrEP attitude and knowledge measures
- 4) Satisfaction questionnaires collected during enrollment and 30 , 60, and 90-day follow-up
- 5) Laboratory reports obtained from the patient's electronic medical record at enrollment and 30 and 90-day follow-up
- 6) Locator forms collected to obtain correct contact information collected at enrollment and 30 and 60 day follow up
- 7) VSQ-9 study visit questionnaires collected at 30 and 90-day follow-up
- 8) Adherence questionnaires collected at 30, 60, and 90-day follow-up
- 9) Facility follow-up questionnaire

Data for Aim 1 will be collected using a touch screen tablet and paper and pencil surveys administered by the RA. All data will be linked to the individual study participant but will be de-identified for analysis.

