21.0 Outcome measures

Secondary Outcome 1:	Retention in PrEP care at 30, 60, and 90 days post PrEP index visit
Type	Secondary
Time frame	30, 60 and 90 days
Description	# of patients retained in care at 30, 60 and 60-days post-PrEP initiation

Secondary Outcome 2: PrEP usage post PrEP index visit

Type	Secondary
Time frame	30, 60 and 90 days
Brief description	# of patients still using PrEP at 30 and 60-days post PrEP initiation

Secondary Outcome 3:	PrEP adherence at follow up post PrEP index visit
Type	Secondary
Time frame	30, 60, 90 days
Brief description	Level of adherence to PrEP at 30, 60, 90-days post PrEP initiation

Secondary Outcome 4:	Risk behavior post PrEP index visit
Type	Secondary
Time frame	30, 60, 90 days
Brief description	HIV risk behaviors at 30, 60, 90-days post PrEP initiation

Secondary Outcome 5:	STI diagnoses post PrEP index visit
Type	Secondary
Time frame	30, 60, 90 days
Brief description	# and type of STI diagnosed at 30 and 90-day post PrEP initiation visits

Secondary Outcome 6:	HIV infection
Type	Secondary
Time frame	90-days
Brief description	# of new HIV infections, if any, at 90-days post PrEP initiation

Secondary Outcome 7:	Program Satisfaction
Type	Secondary
Time frame	90-days
Brief description	Program satisfaction at 30, 60 and 90-day follow-up

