Appendix 5: PrEP Screening for Substantial Risk and Eligibility (ICAP)

Pre-Exposure Prophylaxis (PrEP) Screening for Substantial Risk and Eligibility

1. Facility Information		
Facility Name		
Date of Initial Client Visit (dd/mm/yyyy) ____ / ____ / ____	Person Completing Form	
/ ____ / ____		
2. Client Information		
First Name	Middle Name	Surname
Address	Telephone #	

Client ID Number

3. Client Demographics

What was your sex at birth?	 Male  Female  No response	 Other (specify): _____
What is your current gender?	 Male  Female  Transgender (male to female)  Transgender (female to male)  Other (specify): _____	 Transgender
What is your age? (Specify number of years.)	_____	

4. Screening for Substantial Risk for HIV Infection

Client is at substantial risk if he/she belongs to categories ①, ②, or ③ below	Question Prompts for Providers
① If client is sexually active in a high HIV prevalence population PLUS reports ANY one of the below in the last 6 months	Have you been sexually active in the last 6 months?
 Reports vaginal or anal intercourse without condoms with more than one partner	In the last 6 months, how many people did you have vaginal or anal sex with? In the last 6 months, did you use condoms consistently during sex?
 Has a sex partner with one or more HIV risk:	In the last 6 months, have you had a sex partner who: 
 • Is living with HIV? • Injects drugs? • Has sex with men? • Is a transgender person? • Is a sex worker? • Has sex with multiple partners without condoms?

 History of a sexually transmitted infection (STI) based on self-report, lab test, syndromic STI treatment	In the last 6 months, have you had an STI?
 History of use of post-exposure prophylaxis (PEP)	In the last 6 months, have you taken post-exposure prophylaxis (PEP) following a potential exposure to HIV?
② If client reports history of sharing injection material or equipment in the last 6 months  History of sharing injection material or equipment	In the last 6 months, have you shared injecting material with other people?

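### STI diagnosis is compared between arms as yes/no although follow-up testing happens only in clinical care, so a difference in retention can produce a difference in recorded STIs with no true effect

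*Combined protocol and SAP*

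**What the plan says.** **Testing after discharge.** Section 9.3 says "We do not anticipate the need for any re-testing (HIV, LFTs, eCrCL) by the study team after ED discharge". The bracket does not name STIs, but the same paragraph then covers all testing: "All recommended follow-up testing will be the responsibility of the clinical PrEP provider". Section 9.5 adds "All follow-up assessments will be performed over the phone", so study contacts yield no specimens. Section 12.4 says the investigators will not direct outpatient care. They expect HIV tests every 3 months and STI tests when there are signs or symptoms.

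**Sources of STI data.** Section 12.2 lists laboratory reports from the "electronic medical record at enrollment and 30 and 90-day follow-up". Section 9.5 also repeats ICAP Section 4 at each call, with the item "In the last 6 months, have you had an STI". It lists the CDC Sexual Behavior Questions (CSBQ) as well, whose second tier asks about STI diagnoses over 12 months. Section 10.4.14 mentions that questionnaire at enrollment only.

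**Analysis.** Section 11.1.2 says "Retention in care and STI diagnosis will be treated as dichotomous variables for analysis" and sets out to see how the arms differ on it. It gives no rule for participants who were not tested and plans no count of those tested. Section 11.1.1 rules out imputation.

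**Time points.** Section 7.2 lists "STI diagnoses at 30, 60 and 90 day follow-up visits". The Section 21.0 time frame agrees, but its description reads "and type of STI diagnosed at 30 and 90-day post PrEP initiation visits", and 12.2 also lists laboratory reports at 30 and 90 days only.

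**The concern.** A recorded STI needs an infection and a test. The test depends largely on being in care, and being in care is what the starter pack is meant to change. A yes/no comparison that ignores testing therefore mixes incidence with ascertainment. If iPrEP improves retention, that arm can show more STIs simply because more of it was examined, and this could be misread as riskier behavior on PrEP. If iPrEP lowers retention, the distortion reverses.

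The self-report items do not separate the two. They mostly capture diagnoses already made in care. Their 6- and 12-month windows at days 30, 60 and 90 also reach back before enrollment, in a trial that prioritizes patients with STI complaints, so the STI that brought someone to the ED can be counted again at each call.

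Aim 1b says the pilot data will be used to plan a definitive trial. A distorted STI contrast would be carried into that design.

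**Working it through.** **Inputs from the plan.** 40 per arm; control retention 50%; iPrEP retention 55% to 85% (table in 11.1.3, which the protocol calls illustrative).

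**Reproducing the plan's figure.** Exact binomial enumeration of the two-sided pooled Z test with 40 per arm gives power 0.8166 for 50% vs 80% and 0.2859 for 50% vs 65%, as printed. The other five rows also match to four decimals. The retention scenarios below are therefore the plan's own.

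**Assumptions.** The documents give no STI rate, so true 90-day incidence q is assumed, equal in both arms, over 10% to 50%. Untested participants are recorded as no STI. Let r be the share retained in care, and u the share of those not in care who are tested anyway.

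**Formula.** Share tested = r + u(1 − r). Recorded rate = q × share tested. The ratio between arms is the ratio of the shares tested, so q cancels.

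**Only retained participants tested (u = 0).**
- 50% vs 80%: 0.80 / 0.50 = 1.6
- 50% vs 65%: 0.65 / 0.50 = 1.3
- 50% vs 60%: 0.60 / 0.50 = 1.2

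**A quarter of those out of care also tested (u = 0.25), 50% vs 80%.**
- Control: 0.50 + 0.25 × 0.50 = 0.625
- iPrEP: 0.80 + 0.25 × 0.20 = 0.85
- Ratio: 0.85 / 0.625 = 1.36

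**Chance of p ≤ 0.05 with no true effect.** Section 11.1.2 names no test for STI. I used Fisher's exact test, which the plan names for the primary outcome, by exact enumeration at 50% vs 80% retention.

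| q | Recorded, u = 0 | Expected cases of 40 | Fisher, u = 0 | Fisher, both arms 50% tested | Fisher, u = 0.25 |
|---|---|---|---|---|---|
| 10% | 5% vs 8% | 2.0 vs 3.2 | 0.0176 | 0.0040 | 0.0157 |
| 20% | 10% vs 16% | 4.0 vs 6.4 | 0.0696 | 0.0168 | 0.0492 |
| 30% | 15% vs 24% | 6.0 vs 9.6 | 0.1179 | 0.0255 | 0.0725 |
| 50% | 25% vs 40% | 10.0 vs 16.0 | 0.2214 | 0.0287 | 0.1262 |

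At 50% vs 60% with u = 0, Fisher stays below 0.05 for every q in the table (at most 0.0487). The pooled Z test is less conservative: at 50% vs 80% with u = 0 it gives 0.0880, 0.1319, 0.1748 and 0.2936 for the four values of q.

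**Equal testing.** If the share tested is the same in both arms (for example 85% in each), the expected difference is zero.

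**HIV.** At an assumed 1% risk and u = 0, expected detected cases are 40 × 0.01 × 0.50 = 0.2 and 40 × 0.01 × 0.80 = 0.32. No comparison would be informative.

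**The case against.** Several stronger readings are tempting, and the documents do not support them.

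- A reader might infer that the medical record is the only source. It is not. ICAP self-report is scheduled in both arms, and Section 18.4 elicits adverse events at each follow-up, with an onset date on the Appendix 10 form. A new STI could be captured there. What remains is that each route still mostly needs a diagnosis already made, and 11.1.2 names none of them as the STI source.
- A reader might infer that the plan codes untested people as negative. It does not say so. Coding them as missing would give a ratio of 1.0 under the equal-incidence assumption. But that restricts the comparison to a subset selected after randomization, which randomization does not protect. The supportable defect is that testing is not accounted for.
- A reader might take 1.6 as the expected size. It is near the upper end: it needs a 30-point retention gap and no testing outside PrEP care. Section 12.4 expects symptom-driven STI testing, which can happen elsewhere.
- A reader might infer that recounted index STIs favor one arm. Randomization balances them on average, so they add noise and dilute differences.
- A reader might extend the yes/no comparison to HIV. Section 21.0 plans only a count of new infections, and 11.1.2 does not list HIV among the comparisons.

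It is also fair that the outcome is exploratory in a pilot. That lowers the weight of the point. It does not make the contrast interpretable.

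**Conclusion.** The point holds for STI diagnosis. Ascertainment depends on care attendance, the intervention aims to change care attendance, and the planned yes/no comparison does not account for who was tested. The distortion arises only if retention, and with it testing, differs by arm. That is the trial's hypothesis, not a certainty.

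With equal true incidence and untested participants recorded as no STI, the spurious ratio at 50% vs 80% retention is up to 1.6, and 1.36 if a quarter of those out of care are tested. At 10% incidence the first case is an excess of 1.2 participants of 40 (3.2 − 2.0). Under Fisher's test the error rate passes 5% only with a large retention gap and a high STI rate, so the main harm is a distorted estimate. The HIV count shares the ascertainment limit but has no planned comparison. For an exploratory secondary outcome this should be corrected, but it does not threaten the primary result.

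**What to change.** 1. At each planned call, ask every participant in both arms whether they were tested for, and whether they were diagnosed with, an STI or HIV since the last study contact (since the ED visit at the first call). Use this window for the STI outcome in place of the 6- and 12-month items.
2. In 11.1.2, report the number tested by arm and time point beside diagnoses per participant randomized. Give diagnoses per participant tested only as a descriptive supplement, because those tested are a post-randomization subset.
3. Label the outcome 'STI diagnoses made in care' and make no between-arm claim about incidence.
4. Reconcile the STI time points in 7.2, 12.2 and 21.0.

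The cost is two short questions on three calls already planned, plus analysis wording. No study testing is added. The new questions still capture only diagnoses that someone made, so the outcome stays descriptive, but the reader can see how far testing differed between arms.

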9.4 Randomization

Randomization will occur after the patient signs the informed consent document. The randomization sequence will be obtained by computer-generated random numbers and provided to research associates through a web portal.

9.5 Follow-up

All follow-up assessments will be performed over the phone. Follow-up assessments will occur at 30, 60, and 90 days post enrollment.

Follow-up assessments will include:

- 1) Attitudes toward Pre-Exposure Prophylaxis Scale (APS) (Appendix 3)
- 2) Section 4 of ICAP "Screening for Substantial Risk of HIV" (Appendix 5)
- 3) Satisfaction questionnaire and qualitative assessment and visit specific satisfaction instrument (VSQ-9) (Appendix 6)
- 4) Adherence information measured by (1) self-report. Self-report will be assessed with the single measure Guidelines Regimen Information Program (GRIP) guide and questions on last dose and number of missed doses since prior follow-up. (Appendix 7)
- 5) CDC Sexual Behavior Questions (CSBQ) (Appendix 4)
- 6) STAR*D PRISE (Side-effect assessment)

Assessment of engagement in PrEP care at 30, 60, and 90 days post enrollment will be verified by direct contact with the treatment provider/program provided or by EMR review if the patient is linked within the Mount Sinai Health System. If the patient is receiving their PrEP care outside of the Mount Sinai Health System, a signed release authorization form will be sent.

9.6 Compensation

Because of the expected difficulty of maintaining high follow-up rates in the study population, adequate compensation for time and inconvenience is critical. Compensation of a \$25 gift card will be distributed in-person for completing the enrollment process at the initial ED visit and each follow-up assessment (30, 60, and 90 days).

Participant completes the enrollment and all follow-up all daily assessments the total additional amount could receive would be \$100.

9.7 Standard Intervention for all Participants: PrEP Counseling

All participants initiating PrEP will be provided with standard PrEP counseling by the Emergency Department Health Educator. PrEP counseling includes, (1) how PrEP works, (2) the benefits and risks of PrEP, (3) the need for adherence to the dosing schedule for PrEP to be protective and (4) how other safer sex and safer drug injection practices decrease the risk of acquiring drug-resistant HIV, other sexually transmitted infections (STIs), Hepatitis C virus, and pregnancy.

9.8 PrEP starter packs

14-day starter packs of FTC/TDF and FTC/TAF will be stored in the ED medication dispensing system. Standard operating procedures will be created for storage and dispensing. It should take no more than 5-minutes to retrieve the medication.

10. STUDY ASSESSMENTS

10.1 Overview:

The baseline and follow-up assessments for this study attempt to balance the benefits of comprehensive data collection against the feasibility of collecting data in often chaotic and pressured environment of the Emergency Department.⁷³ A cumbersome assessment process is also likely to impede the successful completion of the study through an adverse effect on recruitment nor would it model real-world clinical practice. If this intervention is to be successful it must not only be shown to be effective but also feasible and pragmatic. Excluding collection of a study patient participant characteristics and locator information, the patient's baseline data will include a brief assessment of HIV risk and attitudes toward PrEP. The total expected time burden for the screening assessments is 30-60 minutes. Assessments collected at 30, 60, and 90 days post study enrollment will be similar.

10.3 Pre-Enrollment (Screening) Assessment Phase

10.3.1 ICAP PrEP Screening Questionnaire

Individuals will meet with an RA to be evaluated for study eligibility. This assessment will be conducted after verbal consent, and before enrollment into the study. It will include questions about PrEP behavioral eligibility criteria.

10.3.4 Patient Eligibility and Inclusion/Exclusion

The Patient Eligibility and Inclusion/Exclusion form collects information regarding eligibility during the screening phase, before written informed consent is obtained. This includes an initial discussion about the availability of two alternate contacts in addition to the participant. Prior to signing consent patients will only be asked if they have two points of additional contact and not the specific information for those contacts.

